10.3 Final Analysis Plan

The purpose of this trial is to estimate AE rates and patterns of immune response as well as to compare these rates and patterns when Na-GST-1/Alhydrogel® and Na-APR-1 (M74)/Alhydrogel® are administered separately or when they are co-administered.

This section briefly describes the statistical methods to be used; a detailed analytical plan will fully describe the methods. The analytical plan will discuss the planned approaches to missing data. Deviations from the original analytical plan will be thoroughly documented and reported to the Sponsor.

Descriptive and hypothesis-testing approaches will be used to meet the protocol objectives as stated in **Section 3**. Estimates will be presented with their 95% confidence intervals. Formal statistical tests, as outlined below, will be used to compare doses. Statistical tests will use a two-sided significance level of 5%.

Primary Objective: To evaluate the safety and reactogenicity of three different dose concentrations of *Na-APR-1* (M74)/Alhydrogel® co-administered with *Na-GST-1*/Alhydrogel® in healthy Gabonese children.

AEs will be coded according to Medical Dictionary of Regulatory Activities (MedDRA™) preferred terms. The frequency, severity, and relationship of AEs per each dose of *Na-APR-1* (M74)/Alhydrogel® and *Na-GST-1*/Alhydrogel® compared to Hepatitis B vaccine will be presented in tabular form using the MedDRA™ coded term and organized by MedDRA™ System, Organ, and Class (SOC) designations.

- The frequency of immediate, systemic, and local injection site AEs will be summarized by SOC and preferred term.
- Line listings of clinical and laboratory AEs classified as immediate (within the first 60 minutes), systemic, and local will be displayed in tables stratified by vaccine (i.e., hookworm vs. Hepatitis B vaccines) dose of *Na-APR-1* (M74)/Alhydrogel® and *Na-GST-1*/Alhydrogel®.
- AEs will be summarized by severity and relationship to vaccine by individuals and dose of *Na-GST-1* and *Na-APR-1* (M74).
- The frequency of vaccine-related SAEs will be tallied as well as summarized by body system, by vaccine and dose.

Primary Outcome Measures:

The following summary parameters will be evaluated for each vaccine (hookworm vs. Hepatitis B) and dose of *Na-APR-1* (M74) co-administered with *Na-GST-1*:

1. Frequency of solicited injection site and systemic reactogenicity, graded by severity, on the day of each study vaccination through 14 days after each study vaccination.
2. Frequency of study vaccine-related serious adverse events from the time of the first study vaccination through approximately 9 months after the last study vaccination.
3. Frequency of clinical safety laboratory adverse events.
4. Frequency of unsolicited adverse events, graded by severity, from the time of each study vaccination through approximately 1 month after each study vaccination.
5. Frequency of new-onset chronic medical conditions through approximately 9 months after the third study vaccination.
6. Frequency of Adverse Events of Special Interest through approximately 9 months after the third study vaccination.

Analysis Plan:

- a. The proportion of participants with at least one injection site AE will be compared by vaccine and dose cohort. We will test the null hypotheses that the type and number of adverse events is the same across all groups by Fisher's exact test.
- b. Laboratory results (hematological and clinical chemistry) will be examined for trends over time and any clinically significant values for individuals will be reported.

Secondary Objective: To determine the doses of co-administered Na-APR-1 (M74) and Na-GST-1 that result in the highest levels of IgG antibody approximately 14 days after the third vaccination.

Secondary Outcome Measure:

The following parameters will be evaluated for each dose of Na-APR-1 (M74) co-administered with Na-GST-1:

1. The IgG level by a qualified indirect ELISA approximately 14 days after the third vaccination.

Analysis Plan:

- a. The proportion of participants with detectable anti-Na-GST-1 and anti-Na-APR-1 (M74) responses will be summarized as a descriptive measure.
- b. IgG levels will be displayed graphically by study group using notched box plots.
- c. Geometric mean antibody responses will be compared between vaccine formulation and dose groups. Comparisons between groups will be made by a one-way analysis of variance (ANOVA) with pair-wise comparisons between groups made by contrasts.
- d. Geometric mean antibody responses for each antigen will be compared using a regression model with main effects for the doses of Na-APR-1 (10, 30 or 100 μ g), and Na-GST-1 (10, 30 or 100 μ g).

Tertiary Objective 1: To assess and compare the duration of antibody responses to Na-GST-1 and Na-APR-1 (M74).

Tertiary Outcome Measure 1: The IgG antibody response, by indirect enzyme-linked immunosorbent assay (ELISA) at approximately 7, 14, and 28 days after each vaccination, and approximately 3 and 6 months after the third dose.

Analysis Plan:

- a. The proportion of participants with detectable anti-Na-GST-1 and anti-Na-APR-1 (M74) responses will be summarized as a descriptive measure.
- b. Antigen-specific IgG levels will be displayed graphically by study group using notched box plots at each time point.
- c. Geometric mean antibody responses will be compared between vaccine and dose groups at each time point. Comparisons between groups will be made by a one-way

analysis of variance (ANOVA) with pair-wise comparisons between groups made by contrasts.

- d. Percent change in IgG antibody levels from days of vaccination to days 7, 14 and 28 will be compared between vaccine formulation and dose groups. Values will be reported with 95% confidence intervals.
- e. Percent change in IgG antibody levels from vaccination day #1 to #2, and from vaccination day #2 to #3 will be compared between vaccine formulation and dose groups to assess the sustainability of the response from trough to trough. Values will be reported with 95% confidence intervals.
- f. Percent change in IgG antibody levels from the peak following the third vaccination, to 3 and 6 months after the third vaccination. Values will be reported with 95% confidence intervals.
- g. Geometric mean antibody responses for each antigen will be compared using a regression model at each time point with main effects for the doses of *Na-APR-1* (M74) (10, 30 or 100 μ g) and *Na-GST-1* (10, 30 or 100 μ g)
- h. A longitudinal model will be built to describe the IgG levels over time. Using a longitudinal panel model, differences in antibody isotype levels by dose of *Na-APR-1* (M74) and *Na-GST-1* will be explored. This will take account of the correlation between measurements on the same participant.

Tertiary Objective 2: To assess the distribution of IgG subclass responses to *Na-APR-1* (M74) and *Na-GST-1*.

Tertiary Outcome Measure 2: The IgG subclass distribution (IgG1, IgG3, and IgG4) by indirect ELISA approximately 14 days after the third vaccination.

Tertiary Outcome Measure 3: The IgG1-4 subclass distribution by ELISA on each day of vaccination, approximately 28 days later, and approximately 3 and 6 months after the final vaccination.

Analysis Plan:

- a. The proportion of subjects with detectable anti-*Na-GST-1* and anti-*Na-APR-1* (M74) IgG1-4 subclass responses will be summarized at each time point as a descriptive measure.
- b. IgG1-4 subclass antibody levels will be displayed graphically by study group using notched box plots at each time point.
- c. Geometric mean antibody responses will be compared between vaccine and dose groups. Comparisons between groups will be made by a one-way analysis of variance (ANOVA) with pair-wise comparisons between groups made by contrasts.
- d. A longitudinal model will be built to describe each of the antibody isotype levels over time for each of IgG1-IgG4. Using a longitudinal panel model, differences in antibody isotype levels by dose of *Na-APR-1* (M74) and *Na-GST-1* will be explored. This will take account of the correlation between measurements on the same participant.

Exploratory Objective 1: To assess the cellular immune responses to the *Na-GST-1* and *Na-APR-1* (M74) antigens following vaccination.

The following assays will be performed to assess the cellular immune responses to vaccination with *Na-APR-1* (M74) +/- *Na-GST-1*:

- a. Lymphocyte proliferative responses to *in vitro* stimulation with *Na-GST-1* or *Na-APR-1* (M74).
- b. Cytokine and chemokine production *in vitro* in response to stimulation with *Na-GST-1* or *Na-APR-1* (M74).
- c. Changes in *in vivo* PBMC subpopulations as determined by flow cytometry.
- d. A longitudinal panel analysis will examine for trends over time.

Exploratory Objective 2: To assess the impact of co-administered *Na-GST-1* and *Na-APR-1* (M74) on the production of memory B cells specific for each antigen.

- a. The percentage of specific memory B cells will be displayed graphically by study group at each time point.
- b. Two separate longitudinal panel analyses will test the null hypothesis that average percentages for each of memory B cells are the same in groups over time. This will take account of the correlation between measurements on the same participant.
- c. Mann-Whitney tests will assess the null hypothesis that cytokine levels are the same in the groups at the primary time point two weeks after final vaccination.

Exploratory Objective 3: To assess the production of memory B cells specific for each vaccine antigen compared to metabolomic changes before and after vaccination.

Exploratory studies will be performed of changes in the metabolomic profiles in response to vaccination using urine samples that will be analyzed using LC-MS. Data will be analyzed using multivariate modeling and multilevel data analysis pipeline.

Should the study be terminated early, the investigative team will discuss with the SMC the reason for termination and determine which study questions can be addressed in an unbiased manner with the available data. The available data will be analyzed and interpreted in light of early termination.

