1.1.2 Clinical Experience with Aluminum-Based Adjuvants

Several licensed vaccines contain aluminum-based adjuvants, including the recombinant hepatitis B vaccine, the tetanus toxoid vaccine, and the diphtheria-tetanus toxoids vaccine.(38, 39) For these aluminum hydroxide-adsorbed vaccines, local reactions such as pain, tenderness, and swelling are experienced in between 7.6% and 16.7% of volunteers in studies that included over 1,200 healthy adults. Fever is seen in 3.2% to 9.3%, headache in 4.1%, and other systemic symptoms such as fatigue, malaise, nausea, and diarrhea at lower frequencies. Urticaria has been reported in 0.1% of individuals vaccinated with the hepatitis B vaccine.

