1.2.3 Clinical Development Plan for the Human Hookworm Vaccine

The target population for the human hookworm vaccine is children 10 years of age or younger living in hookworm endemic areas, since this is the age group that is most at risk of disease from this infection. Prior to conducting clinical trials in this age group, however, both *Na-GST-1* and *Na-APR-1* (M74) are currently being tested in healthy adults living in areas of high hookworm prevalence. Since co-administration of the two antigens in adults has not resulted in any significant safety concerns, testing is proceeding to Phase 1 testing in children living in hookworm endemic areas of Africa (Gabon, as described in this protocol) and Brazil. After safety and immunogenicity of the co-administered products is shown in children, testing of a co-formulated product that contains both *Na-GST-1* and *Na-APR-1* (M74) will be started, first in adults and then in children. The dose concentrations and components of the co-formulated product will be determined through the cumulative results of the study described in this protocol and the previous Phase 1 trials of these vaccine antigens.

The series of Phase 1 trials in adults and children described above will culminate in a large Phase 2 trial in which the co-formulated antigens will be administered to children living in endemic areas. The hookworm vaccine will be compared to a licensed comparator vaccine to evaluate the impact of mean fecal egg counts as well as a variety of clinical and parasitological endpoints. Assuming that an impact on infection is shown in the Phase 2 trial, that there are no new safety issues that arise due to co-formulation of the antigens, and that combining them into one product does not adversely affect the immunogenicity of either, this product will be tested in a pivotal multi-center Phase 3 trial in children. The primary endpoint of the Phase 3 trial will be the incidence of moderate and heavy hookworm infection (as determined by fecal egg counts) following administration of an anthelmintic and vaccination.

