3 STUDY DESIGN

The study will be conducted as a randomized, placebo-controlled, double-blind Phase 1 dose-escalating clinical trial in healthy children between the ages of 6 and 10 years, inclusive, living in the hookworm-endemic area of Lambaréné, Gabon. The study is designed to evaluate the safety, reactogenicity, and immunogenicity of Na-GST-1/Alhydrogel® co-administered with Na-APR-1 (M74)/Alhydrogel®, as compared to the hepatitis B vaccine, in this age group.

Prior to beginning study-related activities, the consent and cooperation of representative community members will be sought, after which parents of potential pediatric participants will be invited to learn about the study and consent to the participation of their child. After a parent or legal representative provides written informed consent for the child's participation and passes the informed consent comprehension questionnaire, the child will undergo eligibility screening, including a complete medical history, physical examination, hematology testing, liver and renal function testing, HIV antibody testing, Hepatitis B and C serology, and urinalysis. In addition, a fecal examination will be performed for ova and parasites, and urine will be examined for *S. haematobium* ova. All clinically significant abnormalities will be reviewed with parents/legal guardians and referral of the child for follow-up care will be provided. After screening, those children determined to be eligible, based on the inclusion and exclusion criteria, will be invited to participate in the study.

Sixty children will be progressively enrolled into 1 of 3 Groups over a projected 3-month enrollment period, with each child followed for 9 months after the final injection (i.e., until Study Day 380 for those receiving vaccinations according to a 0,2,4-month schedule and until Study Day 448 for those receiving vaccinations according to a 0,2,6-month schedule). Group enrollment will be done in an open sequential fashion, whereas within each Group, investigational product (IP) assignment and vaccination will be done in a randomized double-blind fashion.

60 subjects will be enrolled into 3 groups of 20:

The first 20 subjects will be recruited and enrolled into Group 1:

- Group 1 double-blind IP allocation (n=20):
 - 16 subjects will receive 10µg Na-APR-1 (M74) plus 5µg GLA-AF delivered by IM injection in the deltoid muscle, with 10µg Na-GST-1 administered IM in the alternate arm.

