4.3.2 Allocation of vaccination schedule and vaccine randomization

Within each cohort the first 10 participants will receive the 0,2,4-month vaccination schedule and the last 10 will receive the 0,2,6-month schedule. The participants will be randomized to either the experimental group, receiving *Na-APR-1*(M74) plus 5 µg GLA-AF co-administered with *Na-GST-1*, or randomized to the control group who will receive HBV co-administered with sterile saline. In addition, there will be a randomization to assign left/right arm vaccination for the first injection, the arms will be alternated for the second and third sets of vaccinations. The Randomization list will thus only be used on Day 0 for a particular participant.

The vaccination manager assigns the Study ID when the vaccines are being prepared for that particular participant. The Study ID is written onto the syringes and then the vaccinator writes the Study ID onto the CRF.

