enhance the stability and solubility of Na-GST-1. The maximum dose that will be administered is 100 µg of Na-GST-1, or 1.0 ml of the final drug product. This volume contains the equivalent of approximately 400 µg aluminum. Lower doses of Na-GST-1 are delivered by injecting smaller volumes of the 0.1 mg/ml suspension: for example, 0.3 ml will be injected to deliver 30 µg Na-GST-1. For all doses, the ratio of Na-GST-1 to Alhydrogel® will therefore remain constant: for the 30 and 100 µg doses of Na-GST-1 the respective amounts of Alhydrogel® will be 240 and 800 µg (corresponding to approximately 120 and 400 µg aluminum, respectively). Na-GST-1/Alhydrogel® was manufactured, formulated and vailed at Aeras Global Vaccine Foundation (Rockville, Maryland, USA).

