5.1.2.4 Saline Placebo

Sterile isotonic (0.9%) sodium chloride solution ("normal saline") for injection will be procured by the study site. Normal saline is a clear liquid. In study subjects randomized to receive Hepatitis B vaccine, normal saline will be administered intramuscularly as placebo in an equal volume to the Hepatitis B vaccine. It will be administered in the deltoid muscle of the arm opposite to the one in which the Hepatitis B vaccine is delivered so that all study subjects receive two injections on each day of vaccination, thus maintaining the study blind.

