5.1.2.5 Hepatitis B Vaccine

The Hepatitis B vaccine is a non-infectious subunit viral vaccine derived from hepatitis B surface antigen (HBsAg) produced in yeast cells. The antigen is harvested and purified from fermentation cultures of a genetically modified strain of yeast containing the gene for HBsAg. The purified protein is then adjuvanted with aluminum hydroxide adjuvant. The hepatitis B vaccine is a slightly turbid sterile suspension for intramuscular injection. The vaccine is supplied in single-dose vials, with each vial containing enough vaccine to deliver one 0.5 mL dose. Each 0.5 mL dose contains 10 µg of HBsAg and 250 µg of aluminum as aluminum hydroxide. The product conforms to established requirements for sterility, safety, and identity.

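### Local reactions are compared only per child, so the analysis as written cannot attribute them to either product, although opposite-arm injection with randomised side would allow it.

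*Combined protocol and SAP*

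**What the plan says.** **Design.** In all three groups of Section 3, 16 children receive Na-APR-1 (M74) plus 5 µg GLA-AF in one deltoid, with "Na-GST-1 administered IM in the alternate arm", at matched antigen doses of 10/10, 30/30 and 100/100 µg. Four children per group receive hepatitis B vaccine in one arm and saline in the other. Section 5.1.2.4 gives the reason for the saline: "so that all study subjects receive two injections on each day of vaccination, thus maintaining the study blind". On side, Section 4.3.2 says "there will be a randomization to assign left/right arm vaccination for the first injection", with arms alternated at the second and third vaccinations.

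**Analysis.** Solicited injection site reactogenicity belongs to the first primary outcome (Section 2.2.1). Section 10.3, item (a), states: "The proportion of participants with at least one injection site AE will be compared by vaccine and dose cohort", with Fisher's exact test across groups. The interim safety review (Section 10.2.1) uses the same per-child endpoint. The remaining safety output in Section 10.3 is organised by MedDRA class and term, severity, relationship, vaccine group and dose, plus line listings. None of it is said to be by arm, injection or product. Section 8.2.2 treats every local reaction within 14 days as related to vaccination, without naming a product. The visit descriptions in Section 6.3 call for the injection site to be examined but do not ask for the side of a reaction to be recorded.

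**Use of the results.** Section 1.2.3 says: "The dose concentrations and components of the co-formulated product will be determined through the cumulative results of the study described in this protocol". The same sentence adds the previous Phase 1 trials as a source.

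**The concern.** The trial randomises side and separates the two products by arm, and then plans no summary that uses either feature. A child with a reaction in the Na-APR-1/GLA-AF arm and a child with the same reaction in the Na-GST-1 arm count identically. Grouping by dose does not help, because in Section 3 the two doses rise together.

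If local reactions turn out to be frequent, the planned tables would not show whether one injection or both were responsible. That is relevant to choosing the components of a co-formulated product, which this trial is meant to inform.

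Interpretation is also at stake. Hookworm vaccinees have two active injection sites and controls have one plus saline. A higher per-child proportion in vaccinees is a true statement about the regimen, but it says nothing direct about either injection compared with a hepatitis B injection. No per-injection table is planned that would keep the two readings apart.

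**Working it through.** The plan gives no figure for local reactions by product, so there is none to reproduce on this point. The detection table in Section 10.1 is not disputed (for example 1 − 0.90^20 = 87.84%, as stated). All product-specific rates below are assumptions.

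**1. The per-child endpoint does not identify the product rates.** Let pA and pG be the site rates for Na-APR-1/GLA-AF and Na-GST-1, with independent arms. The per-child rate is 1 − (1 − pA)(1 − pG).

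| pA | pG | Per child |
|---|---|---|
| 50% | 0% | 50% |
| 40% | 16.7% | 50% |
| 29.3% | 29.3% | 50% |
| 0% | 50% | 50% |

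**2. Two active sites against one.** The section on aluminium-based adjuvants says local reactions "are experienced in between 7.6% and 16.7% of volunteers", in adult studies. Purely as an illustration, use those figures as a common rate p per active injection, with saline rate s and independent arms. Vaccinees: 1 − (1 − p)². Controls: 1 − (1 − p)(1 − s).

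| p | Vaccinees | Controls, s = 0 | Controls, s = 5% |
|---|---|---|---|
| 7.6% | 1 − 0.924² = 14.6% | 7.6% | 1 − 0.924 × 0.95 = 12.2% |
| 16.7% | 1 − 0.833² = 30.6% | 16.7% | 1 − 0.833 × 0.95 = 20.9% |

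The ratio runs from 14.6/12.2 = 1.2 to 14.6/7.6 = 1.9 with identical reactogenicity per injection. It shrinks as reactions in the two arms correlate. Over three vaccinations with s = 0, the figures are 37.8% v 21.1% and 66.6% v 42.2%.

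An equal rate per injection is itself doubtful. The control injection holds "250 µg of aluminum as aluminum hydroxide". For 1.0 ml (100 µg antigen) of either hookworm product, Section 5.1.2 states: "This volume contains the equivalent of approximately 400 µg aluminum". In proportion, each hookworm injection carries about 40, 120 or 400 µg at 10, 30 or 100 µg antigen, or 80, 240 or 800 µg per visit.

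**3. What a paired contrast could show.** With independent arms, the discordant probabilities are b = pA(1 − pG) and c = pG(1 − pA). Exact two-sided McNemar power at 5%, one vaccination day:

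| Assumed pA v pG | n=16 (one dose) | n=48 (pooled) |
|---|---|---|
| 50% v 20% | 27% | 82% |
| 30% v 10% | 11% | 61% |
| 40% v 20% | 11% | 48% |
| 20% v 10% | 2% | 19% |
| 16.7% v 7.6% | 1% | about 17% |

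With the discordant probabilities (b v c) assumed directly, power at n=48 is 53% (30% v 10%), 70% (35% v 10%) and 84% (30% v 5%). At n=16 it is 11% to 20%. Significance needs at least six discordant pairs, all in one direction: 2 × 0.5^6 = 0.031, while five give 0.0625.

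**4. Precision of the paired difference.** The approximate 95% half-width is 1.96 × √[(b + c − (b − c)²)/n]. For 50% v 20%, b = 0.40 and c = 0.10. At n=48 this gives 1.96 × √(0.41/48) = 0.18, so 30 ± 18 points. For 16.7% v 7.6%, b = 0.154 and c = 0.063. The difference is 9.1 ± 12.9 points at n=48 and 9.1 ± 22.4 at n=16.

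**The case against.** **The per-child contrast matches the objective.** The primary objective concerns the co-administered products, and the comparison in Section 10.2.1 is co-administration against hepatitis B vaccine. A child given the regimen does receive two active injections, and saline is there for the blind. A reader might infer from step 2 that the comparison is biased or should be replaced. The documents do not support that: it is a valid whole-regimen comparison, and no per-injection claim is planned. What stands is a caution about interpretation.

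**The design allows attribution.** A reader might infer that the trial is incapable of saying which product causes local reactions. That goes too far. Products are in opposite arms, the list codes side, sites are examined, and the Safety Monitoring Committee and medical monitor can access the code. The CRF is not in the documents and may already capture side. Section 10.3 also defers full methods to a detailed analytical plan. The gap is in the analysis as written. A later plan could close it, but only if side is recorded at the visit.

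**Other evidence exists.** Section 1.2.3 also relies on previous Phase 1 trials, which tested each product without the other (Sections 1.1.6 and 1.1.9). Component choice does not rest on this trial alone.

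**The contrast does not isolate GLA-AF.** A reader might take a between-arm difference as the adjuvant's effect. Antigen, GLA-AF and buffer (Empigen BB against glucose) all differ between arms, so it compares whole injections.

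**Power is low, and Section 10.1 disclaims it.** This stands. It argues for estimation and against by-dose tests, but not against tabulating by product.

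**Conclusion.** The point holds as a gap in the planned analysis. With local reactions counted per child and matched antigen doses in every group, the output described in Section 10.3 cannot attribute local reactions to Na-APR-1/GLA-AF or to Na-GST-1. The randomised side and opposite-arm injection would permit this once side is recorded and linked.

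The per-child comparison remains valid as regimen burden. Under equal per-injection rates it could show a ratio of about 1.2 to 1.9 by having two active sites instead of one. That range assumes that adult per-volunteer percentages serve as per-injection rates in children, that arms are independent, that saline reacts in 0% to 5%, and that unequal aluminium content does not matter. It illustrates the direction of the effect and does not predict its size.

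The gain from the addition is moderate. Pooled over 48 children, a large difference such as 50% v 20% would probably be seen (82% power), while 16.7% v 7.6% would usually be missed (about 17%).

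One dependency should be noted. The synopsis description of interventions says Na-GST-1 will be tested only at 100 µg, which contradicts the matched doses in the group listings and Section 3. This point uses Section 3, and the passages must be reconciled. The absence of any summary by arm or product does not depend on which applies.

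**What to change.** 1. Record the arm for each solicited local reaction at each vaccination, if the CRF does not already do so. Link it to product at unblinding, using the Day 0 side assignment and the planned alternation.
2. Add to Section 10.3, item (a), a table of local reaction rates per injection with 95% confidence intervals for all four products. With full vaccination this gives 48 × 3 = 144 injections for each hookworm product and 12 × 3 = 36 each for hepatitis B vaccine and saline. Intervals should allow for repeated injections in the same child.
3. Add a paired within-child difference, Na-APR-1/GLA-AF arm minus Na-GST-1 arm, pooled over the 48 vaccinees with the child as cluster and presented as an estimate with its interval. Show by-dose results (n=16) descriptively, without tests.
4. Keep the per-child proportion, and state that it describes the whole regimen. State also that the paired difference compares whole injections and does not isolate GLA-AF.

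The cost is at most one CRF field and one table. No visits or samples are added, and blinding is unaffected because the arm code stays with the vaccine manager until unblinding. The downside is low power unless the arms differ strongly. The side field needs to be in place before the first vaccination; the table can go in the detailed analytical plan.
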